7.12 Dosage and Administration

Administration of pazopanib with a high-fat or low-fat meal results in an approximately 2-fold increase in area under the plasma drug concentration curve (AUC) and maximum observed plasma drug concentration (C_{max}).

Pazopanib should be taken orally without food at least one hour before or two hours after a meal. The tablets should be swallowed whole and must not be crushed or broken. The time of day the tablets are taken should be relatively constant.

If a dose is missed, the subject should take the dose as soon as possible, but only if there are 12 or more hours remaining before the next dose is due. If the next dose is due in less than 12 hours, the subject should skip the missed dose and take the next dose as scheduled.

If vomiting occurs after taking pazopanib, the subject should not take a replacement dose on that day. The subject should resume taking pazopanib at the next scheduled dose on the following day. If vomiting persists, the subject should be instructed to notify the investigator.

As a general rule, if dose reduction of pazopanib is necessary, the dose should be reduced stepwise by 200 mg at each step, and the subject should be monitored for approximately 10 to 14 days at each dose level. If toxicity does not abate during this monitoring time, the medication may need to be interrupted and/or the dose further decreased with continued monitoring for an additional 10-14 days at each dose level, and so on.

If the toxicity has abated with reduction of the dose and dose re-escalation is considered safe by the investigator, the dose can then be increased step-wise back to the pre-event dose (in 200 mg increments, after monitoring for 10-14 days at each dose level to ensure that toxicity did not recur or worsen).

If a subject's treatment has been interrupted for more than 21 days, the Investigator must contact the Study Physician to review the subject's condition in order to resume the treatment.

- 7.2 Patients can be instructed in administration techniques and granted treatment independence with nursing staff approval.
- 7.3 For this protocol, the patient must return to Mayo Rochester, Florida, or Arizona for evaluation at least every 28 days (+/- 3 days).

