8.0 Dosage Modification Based on Adverse Events

8.1 Pazopanib

8.11 Pazopanib Dose Reduction Levels

Starting Dose	800 mg once daily
Dose Level -1	600 mg once daily
Dose Level -2	400 mg once daily

8.12

→ → Use the NCI Common Terminology Criteria for Adverse Events (CTCAE) version 4.0* unless otherwise specified ← ←			
CTCAE System/Organ/Class (SOC)	ADVERSE EVENT	AGENT	ACTION**
BASED ON INTERVAL ADVERSE EVENT			
Investigations	Platelet count decreased Grade 3 or 4	Pazopanib	Omit until ≤ 2 then restart at next lower dose level. If no recovery to grade 2, discontinue
Investigations	Electrocardiogram QT corrected interval prolonged ≥ 500 msec Grade 3	Pazopanib	Discontinue pazopanib
Renal and urinary disorders	Creatinine \geq Grade 3	Pazopanib	Omit until < 3 then restart at next lower dose level. If ≥ 3 recurs, reduce one dose level again until no dose can be given

→ → Use the NCI Common Terminology Criteria for Adverse Events (CTCAE) version 4.0* unless otherwise specified ← ←			
CTCAE System/Organ/Class (SOC)	ADVERSE EVENT	AGENT	ACTION**
Vascular disorders	Thromboembolic event DVT/PE Grade 3	Pazopanib	Omit and initiate anticoagulant. Restart at reduced dose if 
 • Subject must have been treated at desired level of anticoagulation for at least 1 week • No Grade 3 or 4 or clinically significant Grade 2, hemorrhagic events have occurred while on anticoagulation treatment. Note: When treating with warfarin, INR S/B monitored within 3 to 5 days after any change in pazopanib dosing and then at least weekly until INR is stable. The dose of warfarin may need to be adjusted to maintain the desired level of anticoagulation.
	Grade 4 Arterial Thrombosis/Ischemia Any Grade		Discontinue pazopanib Discontinue pazopanib
Vascular disorders	Hypertension	Pazopanib	See table 8.2
Gastrointestinal disorders	Any GI bleed Grade 2-4	Pazopanib	Discontinue pazopanib
Respiratory, thoracic and mediastinal disorders	Any Pulmonary bleed Grade 2-4	Pazopanib	Discontinue pazopanib
Dermatology/ Skin	Dermatitis Grade 2 skin changes w/pain, limiting ADL's Grade3 severe skin changes w/pain Limiting self care ADL's	Pazopanib	Omit until ≤ 1 , then restart at next lower dose level. If recurrent, reduce by another dose level or discontinue Discontinue

→ → Use the NCI Common Terminology Criteria for Adverse Events (CTCAE) version 4.0* unless otherwise specified ← ←			
CTCAE System/Organ/Class (SOC)	ADVERSE EVENT	AGENT	ACTION**

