8.2 Pazopanib-at time of retreatment

→ → Use the NCI Common Terminology Criteria for Adverse Events (CTCAE) version 4.0* unless otherwise specified ← ←			
CTCAE System/Organ/Class (SOC)	ADVERSE EVENT	AGENT	ACTION**
AT TIME OF RETREATMENT			
Investigations	Platelet count decreased Grade 3 or 4	Pazopanib	Hold until ≤ 2 then restart at next lower dose level. If no recovery to grade 2, discontinue
Investigations	Electrocardiogram QT corrected interval prolonged ≥ 500msec Grade 3	Pazopanib	Discontinue pazopanib
Renal and urinary disorders	Creatinine > Grade 3	Pazopanib	Hold until < 3 then restart at next lower dose level. If ≥ 3 recurs, dose reduce again until no dose can be given

→ → Use the NCI Common Terminology Criteria for Adverse Events (CTCAE) version 4.0* unless otherwise specified ← ←			
CTCAE System/Organ/Class (SOC)	ADVERSE EVENT	AGENT	ACTION**
Vascular disorders	Thromboembolic event DVT/PE Grade 3	Pazopanib	Hold and initiate anticoagulant. Decrease 1 dose level if 
 • Subject must have been treated at desired level of anticoagulation for at least 1 week • No Grade 3 or 4 or clinically significant Grade 2, hemorrhagic events have occurred while on anticoagulation treatment. Note: When treating with warfarin, INR S/B monitored within 3 to 5 days after any change in pazopanib dosing and then at least weekly until INR is stable. The dose of warfarin may need to be adjusted to maintain the desired level of anticoagulation.
	Grade 4		Discontinue pazopanib
	Arterial Thrombosis/Ischemia Any Grade		Discontinue pazopanib
Vascular disorders	Hypertension	Pazopanib	See table 8.3
Gastrointestinal disorders	Any GI bleed Grade 2-4	Pazopanib	Discontinue pazopanib
Respiratory, thoracic and mediastinal disorders	Any Pulmonary bleed Grade 2-4	Pazopanib	Discontinue pazopanib
Dermatology/ Skin	Dermatitis Grade 2 skin changes w/pain, limiting ADL's Grade3 severe skin changes w/pain Limiting self care ADL's	Pazopanib	Hold until ≤ 1 , then restart at next lower dose level. If recurrent. reduce by another dose level or discontinue Discontinue

→ → Use the NCI Common Terminology Criteria for Adverse Events (CTCAE) version 4.0* unless otherwise specified ← ←			
CTCAE System/Organ/Class (SOC)	ADVERSE EVENT	AGENT	ACTION**
All Other	Grade 2 or 3, if clinically significant Grade 4	Pazopanib	Hold until ≤ 1 Discontinue pazopanib

* Located at

http://ctep.cancer.gov/protocolDevelopment/electronic_applications.ctc.htm

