Grade 1	For hemoptysis, interrupt pazopanib and contact the Novartis Study Physician to discuss whether further treatment with pazopanib is appropriate. For other Grade I hemorrhage/bleeding events, continue pazopanib at the current dose; monitor as clinically indicated.
Grade 2	Step 1. If pulmonary or GI bleed (other than hemorrhoidal bleeding), discontinue pazopanib and continue follow-up per protocol. Otherwise, interrupt pazopanib until the AE resolved to \leq Grade 1. Step 2. Restart pazopanib ; consider reducing dose and monitor as clinically indicated.
Grade 3 or 4, or Recurrent \geq Grade 2 event after dose interruption/reduction.	Discontinue pazopanib and continue with follow-up per protocol.
Venous Thrombosis (DVT, PE)	
Grade 2	Continue pazopanib at the current dose; monitor as clinically indicated
Grade 3	Step 1. Interrupt pazopanib . Step 2. Initiate and monitor anticoagulation as clinically indicated. Step 3. Resume pazopanib at reduced dose only if all of the following criteria are met: 
 • The subject must have been treated with anticoagulant at the desired level of anticoagulation for at least one week. • No Grade 3 or 4 or clinically significant Grade 2, hemorrhagic events have occurred while on anticoagulation treatment. Subject should be monitored as clinically indicated during anticoagulation treatment and after resuming study treatment. When treating with warfarin, international normalized ratio (INR) should be monitored within three to five days after any change in pazopanib dosing (eg, re-initiating, escalating/de-escalating, or discontinuing pazopanib), and then at least weekly until the INR is stable. The dose of warfarin (or its derivatives) may need to be adjusted to maintain the desired level of anticoagulation
Grade 4 and/or PE	Discontinue pazopanib and continue follow-up per protocol.
Arterial Thrombosis/Ischemia	
Any Grade	Discontinue pazopanib and continue follow-up per protocol.
Thrombocytopenia: Investigate and document underlying cause	
Grade 1 or 2	Continue pazopanib with current dose; monitor as clinically indicated.
Grade 3 or 4	Step 1. Interrupt pazopanib until toxicity resolves to \leq Grade 2.

	Step 2. Restart pazopanib dose-reduced by 200 mg and monitor as clinically indicated. If no recovery to \leq Grade 2 or recurrent Grade 3 or 4 thrombocytopenia, discontinue IP and follow-up per protocol.

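### The platelet rows in Sections 8.12 and 8.2 leave out the Section 8.3 rule to stop pazopanib when Grade 3 or 4 thrombocytopenia recurs

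*Combined protocol and SAP*

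**What the plan says.** Three places in the protocol give the action for a Grade 3 or 4 fall in platelets.

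- Section 8.12 (interval adverse events): "Omit until ≤ 2 then restart at next lower dose level. If no recovery to grade 2, discontinue".
- Section 8.2 (time of retreatment): "Hold until ≤ 2 then restart at next lower dose level. If no recovery to grade 2, discontinue".
- Section 8.3 (thrombocytopenia): interrupt until Grade 2 or lower, then "Restart pazopanib dose-reduced by 200 mg and monitor as clinically indicated". Treatment ends if there is no such recovery, and also on recurrence: "recurrent Grade 3 or 4 thrombocytopenia, discontinue IP and follow-up per protocol".

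Section 8.11 sets the dose levels at 800, 600 and 400 mg, so a 200 mg reduction is the same as one level. Section 7.12 permits re-escalation after a reduction: once toxicity has abated, and if the investigator considers it safe, "the dose can then be increased step-wise back to the pre-event dose".

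**The concern.** Section 8.3 has two triggers for stopping and the two tables have one. The platelet rows apply to any Grade 3 or 4 event and say to restart one level lower provided the count recovers. A clinician who uses only those tables could therefore re-expose a patient whom 8.3 removes from treatment for a repeated severe toxicity. The incomplete rows are the less cautious ones.

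The misreading is plausible. Neighbouring rows do deal with recurrence, and they allow a further reduction. The creatinine row in 8.12 reads "If ≥ 3 recurs, reduce one dose level again until no dose can be given", and the dermatitis rows offer another reduction or discontinuation. A reader could infer the same for platelets. Blood counts are scheduled on Day 1 of every cycle (Section 4.0), so the retreatment table in 8.2 is a natural one to consult when a recurrence is found.

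**Working it through.** **Comparison of the rules**

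| Situation | 8.12 and 8.2, read literally | 8.3 |
|---|---|---|
| First Grade 3-4 event at 800 mg, recovers | Restart at 600 mg | Restart at 600 mg |
| No recovery to Grade 2 | Discontinue | Discontinue |
| Second event at 600 mg, recovers | Restart at 400 mg | Discontinue |
| Second event at 800 mg after re-escalation under 7.12, recovers | Restart at 600 mg | Discontinue |
| Event at 400 mg | No lower level exists | No lower level; discontinue if recurrent |

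The divergence is confined to a second event that recovers while a lower dose level is still available.

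**Does other text close the gap?**

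- Section 7.4 ends treatment when a severe toxicity prevents restart after a delay of 28 days or more. It does not address recurrence.
- Section 7.12 asks for contact with the Study Physician after an interruption of more than 21 days. It also lets the dose be lowered further if toxicity persists, and lets it be re-escalated. None of this stops treatment on recurrence.
- The Grade 4 stop in the residual row for all other events does not apply, because platelets have their own row.
- The hypertension row of 8.2 points to 8.3. The platelet rows have no such pointer.

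**How many patients**

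The plan states no figure to reproduce. The inputs are the Grade 3 and Grade 4 thrombocytopenia rates on pazopanib in Appendix VIII, with rates given as below 1% entered as 1%, and the sample sizes in Section 16.22: 35 evaluable patients plus 4, so 39.

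Expected first events = (Grade 3 rate + Grade 4 rate) × n, as upper bounds:

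- Renal cell carcinoma (Table 79, below 1% and below 1%): (0.01 + 0.01) × 39 = 0.78; × 35 = 0.70.
- Soft tissue sarcoma (Table 80, 3% and below 1%): (0.03 + 0.01) × 39 = 1.56; × 35 = 1.40.

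The documents give no recurrence rate. Assume that 10% to 50% of first events recur and recover again. Expected patients at the divergent step, n = 39:

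- Renal: 0.78 × 0.10 = 0.078 to 0.78 × 0.50 = 0.39.
- Sarcoma: 1.56 × 0.10 = 0.156 to 1.56 × 0.50 = 0.78.

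Chance of at least one such patient = 1 − (1 − p)^39, where p is the first-event rate times the assumed share:

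- Renal: p = 0.002 to 0.01 gives 7.5% to 32.4%.
- Sarcoma: p = 0.004 to 0.02 gives 14.5% to 54.5%.

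For any given share these are upper bounds, because of the rounding up to 1%.

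**The case against.** The strongest reply is that this is silence, not contradiction. The two rows never tell anyone to re-treat after a recurrence. Section 8.3 repeats their interruption, their reduction and their non-recovery stop, and adds one more stop, so a reader who applies all three follows 8.3. Nor are the tables self-sufficient: the rules for a fall in ejection fraction and for proteinuria appear only in 8.3, so the clinician must consult it anyway. The comparators are also weaker than they look. Creatinine has no entry in 8.3, so its recurrence rule had to sit in the tables, and the hypertension row carries a pointer because it has no action of its own.

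Much of this stands. The complementary reading is available, dermatitis is the fairest comparator, and the sarcoma rates come from a different disease. The recurrence share is assumed, so the upper probabilities should carry little weight. The patient concerned would also have recovered to Grade 2 or lower and would restart on a reduced dose.

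It does not remove the point. The rows are not restricted to a first event, so their restart instruction covers a recovered second one on its face. Nothing gives 8.3 precedence. A stop rule should not depend on the reader finding it in a later section to which the row does not point.

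**Conclusion.** The inconsistency holds and is minor. For a second Grade 3 or 4 event that recovers, with a lower dose level available, the platelet rows of 8.12 and 8.2 followed literally give a less safe action than 8.3. On the first event and on non-recovery the sections agree.

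Few patients, possibly none, would be affected: well under one expected at renal-cancer rates, and still under one at sarcoma rates, even with half of first events assumed to recur and recover. The textual finding does not depend on that assumption.

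The primary analysis does not change. Under Sections 16.11 and 16.311 every eligible, consented patient who begins treatment is evaluable for 12-month survival, and under Section 13.3 those who stop drug for reasons other than progression go to event monitoring.

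**What to change.** In the platelet rows of 8.12 and 8.2, extend the stopping condition to recurrence, for example: *If no recovery to grade 2, or if Grade 3 or 4 recurs, discontinue.* This adopts the protocol's own stricter rule. Alternatively, state in both rows that Section 8.3 governs. Section 8.3 needs no change.

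The cost is one clause in one row of each of two tables, with no effect on assessments, sample size or analysis. It can go into the next amendment.

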8.4 Guidelines for Management of Treatment Emergent Hepatotoxicity

Event	Dose Modification Algorithms
(A). ALT of $\leq 3.0 \times \text{ULN}$	Continue pazopanib at current dose with full panel LFTs ⁰ monitored as per protocol.
(B). ALT $>3.0 \times \text{ULN}$ to $\leq 8.0 \times \text{ULN}$ without bilirubin elevation (defined as total bilirubin ⁰ $<2.0 \times \text{ULN}$ or direct bilirubin $\leq 35\%$) and without hypersensitivity symptoms (e.g., fever, rash)	
Liver Event Monitoring Criteria:
 
(1) Continue pazopanib at current dose levels.
 
(2) Monitor subject closely for clinical signs and symptoms; perform full panel LFTs^a weekly or more frequently if clinically indicated until ALT/AST is reduced to Grade 1.

(C). ALT $>8.0 \times \text{ULN}$ without bilirubin elevation (defined as total bilirubin ^b $<2.0 \times \text{ULN}$ or direct bilirubin $\leq 35\%$) and without hypersensitivity symptoms (e.g., fever, rash)	
1st occurrence – Liver Event Interruption Criteria⁰:
 
(1) Interrupt pazopanib until toxicity resolves to \leqGrade 1 or baseline. Report the event to Novartis as an SAE within 24 hours of learning of its occurrence and complete the eCRF liver event forms. Make every reasonable attempt to have subjects return to the clinic within 24 to 72 hours for repeat liver chemistries and liver event follow up assessments.
 
(2) Liver imaging and other laboratory investigations should be considered as clinically appropriate.
 
(3) Monitor subject closely for clinical signs and symptoms; perform full panel LFTs^a weekly or more frequently if clinically indicated until ALT/AST is reduced to Grade 1.
 
(4) If the subject is benefiting from the study treatment, contact Novartis Study Physician for possible re-challenge. Re-treatment may be considered if ALL following criteria are met:
 
 - ALT/AST reduced to Grade 1 - Total bilirubin $<1.5 \times \text{ULN}$ or direct bilirubin $\leq 35\%$ - No hypersensitivity signs or symptoms - Subject is benefiting from therapy. 
Recurrence – Liver Event Stopping Criteria⁰:
 
Discontinue pazopanib permanently and monitor subject closely for clinical signs and symptoms; perform full panel LFTs^a weekly or more frequently if clinically indicated until ALT/AST is reduced to Grade 1. At the time of the recurrence, complete the eCRF liver event forms.

Event	Dose Modification Algorithms
(D). ALT >3.0 x ULN with concomitant elevation in bilirubin ⁰ (defined as total bilirubin ≥2.0 x ULN; with direct bilirubin >35%) or with hypersensitivity symptoms (e.g., fever, rash).	
Liver Event Stopping Criteria⁰:
 
(1) Discontinue pazopanib immediately, report the event to Novartis as an SAE within 24 hours of learning of its occurrence, and complete the eCRF liver event forms. Make every reasonable attempt to have subjects return to the clinic within 24 hours for repeat liver chemistries and liver event follow up assessments.
 
(2) Consult a gastroenterologist / hepatologist, collect PK sample and perform the following assessments to identify potential co-factors:
 
 - Eosinophil count - Viral serology for hepatitis A, B, C and E, cytomegalovirus, Epstein-Barr virus (IgM antibody, heterophile antibody, or monospot testing) - Anti-nuclear antibody, anti-smooth muscle antibody, Type 1 anti-liver kidney microsomal antibodies. - Serum creatinine phosphokinase for possible muscle injury caused LFT elevation - Liver imaging 
-Consider toxicological blood screen for possible contributing chemical/medical entities
 
(3) Monitor subject closely for clinical signs and symptoms; record the appearance or worsening of clinical symptoms of hepatitis, or hypersensitivity, such as fatigue, nausea, vomiting, right upper quadrant pain or tenderness, fever rash or eosinophilia as relevant on the AE report form. Perform full panel LFTs^a weekly or more frequently if clinically indicated until LFTs are reduced to Grade 1.

For isolated total bilirubin ⁰ elevation without concurrent ALT increases (defined as ALT <3 X ULN).	
(1) Isolated hyperbilirubinemia (i.e., in the absence of elevated ALT or other signs/symptoms of liver injury) does not require dose modification. Pazopanib inhibits UGT1A1 and OATP1B1, which can cause elevation of indirect (unconjugated) bilirubin in the absence of liver injury..
 
(2) If bilirubin is >1.5 x ULN in the absence of ALT elevation, fractionation of bilirubin elevation should be performed. If bilirubin is >35% direct (conjugated), further evaluation for underlying cause of cholestasis should be performed.

- a. Full panel LFTs include: AST, ALT, alkaline phosphatase, GGT, and total bilirubin. Coagulation tests should be performed as clinically indicated.
- b. Serum bilirubin fractionation should be performed if testing is available. If testing is unavailable and a subject meets the criterion of total bilirubin >1.5 x ULN, then the event should be promptly reported as an SAE.
- c. When a liver chemistry event meets the Liver Event Interruption Criteria, or Liver Event Stopping Criteria, blood samples should be obtained for PK and for clinical laboratory testing by the central laboratory (Liver Event Kits will be provided for this purpose).

Abbreviations: ALT alanine aminotransferase; AST aspartate aminotransferase; eCRF electronic case report form; IP investigational product; LFT liver function tests; PK pharmacokinetics; SAE serious adverse event; ULN upper limit of normal

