3.0 Patient Eligibility

3.1 Inclusion Criteria

3.11 Age \geq 18 years

3.12 Histological confirmation of non-clear cell renal cancer (including Chromophilic (papillary), Chromophobic, Oncocytic, sarcomatoid, Collecting duct (Bellini's duct), translocation-type carcinoma or medullary renal cell carcinoma.

3.13 Up to one prior treatment for metastatic non clear cell carcinoma is allowed prior to registration as long as the agent used to treat was not pazopanib.

3.14 Measurable or non-measurable metastatic disease as defined in Section 11.0.

3.15 ECOG Performance Status (PS) 0, 1 or 2 (Appendix II).

3.16 The following laboratory values obtained \leq 14 days prior to registration.

- ANC \geq 1500
- PLT \geq 100,000
- HgB $>$ 9.0 g/dL. NOTE: Subjects may not have had a transfusion within 7 days of registration.)
- Total Bilirubin $<$ 1.5 x ULN
- Alanine amino transferase (ALT) \leq 2.5 X ULN. NOTE: Concomitant elevations in bilirubin and ALT above 1.0 x ULN (upper limit of normal) is not permitted.

- Aspartate aminotransferase (AST) $\leq 2.5 \times$ ULN. Note: Concomitant elevations in bilirubin and AST above $1.0 \times$ ULN (upper limit of normal) is not permitted.
- Urine Protein to Creatinine Ratio (UPC; appropriate appendix) (UPC) < 1
NOTE: If UPC ≥ 1 , then a 24-hour urine protein must be assessed. Subjects must have a 24-hour urine protein value < 1 g to be eligible.
- Prothrombin time (PT) or international normalized ratio (INR) $\leq 1.2 \times$ ULN NOTE: Subjects receiving anticoagulant therapy are eligible if their INR is stable and within the recommended range for the desired level of anticoagulation

3.17 A female is eligible to enter and participate in this study if she is of:

a. Non-childbearing potential (i.e., physiologically incapable of becoming pregnant), including any female who has had:

- A hysterectomy
- A bilateral oophorectomy (ovariectomy)
- A bilateral tubal ligation
- Is post-menopausal

Subjects not using hormone replacement therapy (HRT) must have experienced total cessation of menses for ≥ 1 year and be greater than 45 years in age, OR, in questionable cases, have a follicle stimulating hormone (FSH) value > 40 mIU/mL and an estradiol value < 40 pg/mL (< 140 pmol/L).

Subjects using HRT must have experienced total cessation of menses for ≥ 1 year and be greater than 45 years of age OR have had documented evidence of menopause based on FSH and estradiol concentrations prior to initiation of HRT

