- a) Absorption – Pazopanib is absorbed orally with an absolute oral bioavailability range of 13.5 to 38.9% after an 800 mg dose, with a median absolute bioavailability of 21%. Plasma concentrations of pazopanib peak from 2 to 4 hours following single dose administration. Systemic exposure to pazopanib is increased when administered with food. Administration with a high-fat or low-fat meal results in an approximately 2-fold increase in AUC and C_{max} . Pazopanib should be administered at least one hour before or 2 hours after a meal. Administration of pazopanib as a crushed tablet increases the rate and extent of oral absorption relative to administration of the whole tablet. The crushing of the tablet increases AUC by 46% and C_{max} by approximately 2-fold, but decreases t_{max} by approximately 2 hours relative to administration of the whole tablet. Consequently, it is recommended not to crush pazopanib tablets.
 - b) Distribution – Binding of pazopanib to human plasma protein in vivo was greater than 99% with no concentration dependence. Pazopanib is associated with a small volume of distribution (9.2 to 131L).
 - c) Metabolism – In vitro studies demonstrate pazopanib is metabolized by CYP3A4 with a minor contribution from CYP1A2 and CYP2C8. Patients who have AST/ALT >3 X ULN and concurrent bilirubin >2 X ULN must permanently discontinue pazopanib. Use of pazopanib is not recommended in patients with total bilirubin >3 X ULN (regardless of any ALT) due to insufficient data with this severe impairment.
 - d) Elimination – Pazopanib has a mean half-life of 30.9 hours after administration of an 800mg dose. Elimination is primarily via feces with renal elimination accounting for < 4% of the administered dose.
- 15.16 **Potential Drug Interactions: CYP3A4 Inhibitors and Inducers:** Coadministration of pazopanib with strong inhibitors of CYP3A4 (e.g., itraconazole, atazanavir, indinavir, nefazodone, nelfinavir, saquinavir, telithromycin, voriconazole, ketoconazole, ritonavir, clarithromycin) increases pazopanib concentrations and should be avoided. Grapefruit juice should be avoided as it inhibits CYP3A4 activity and may also increase plasma concentrations of pazopanib. CYP3A4 inducers such as rifampin may decrease plasma pazopanib concentrations. Pazopanib should not be used if chronic use of strong CYP3A4 inducers cannot be avoided. Please see Appendix VI for a list of strong inhibitors and inducers of CYP3A4.

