- 15.26 Due to the similarity in nature of this agent to other VEGF inhibitors (bevacizumab, VEGF-trap, etc.) monitor for signs of bleeding, thrombosis and PE. Instruct patient to report any calf tenderness, shortness of breath, chest pain or bleeding immediately.
- 15.27 Cytopenias are common. Monitor CBC w/diff and instruct patient to report any unusual bruising or bleeding and/or signs of infection to study team.
- 15.28 Monitor LFT's. Patients who have AST/ALT levels > 3x ULN and concurrent bilirubin >2X ULN should permanently discontinue pazopanib. Patients with AST/ALT levels as above and mild hyperbilirubinemia (with suspected or known Gilbert's syndrome) should be monitored weekly while continuing pazopanib.
- 15.29 Cardiac side effects (CHF, MI, chest pain, etc). while rare can be serious and life threatening. Instruct patient to report any cardiac symptoms to study team immediately.
- 15.29a RPLS, CVA, and TIA are uncommon, but are life threatening. Instruct patient to report any neurological symptoms to the study team immediately.

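### If AST/ALT means either enzyme, Section 15.15(c) permanently stops pazopanib for AST >3 x ULN with raised conjugated bilirubin, while Section 8.4 row A continues it whenever ALT is ≤3 x ULN

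*Combined protocol and SAP*

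**What the plan says.** **Section 8.4, dose rules for hepatotoxicity.**
- Row A applies when ALT is at most 3.0 x ULN. Its action is "Continue pazopanib at current dose with full panel LFTs" monitored on schedule. AST and bilirubin do not appear in its trigger.
- Rows B and C require ALT above 3.0 and above 8.0 x ULN respectively.
- Row D, the stopping row, begins "ALT >3.0 x ULN with concomitant elevation in bilirubin". It defines that elevation as total bilirubin of at least 2.0 x ULN with direct bilirubin above 35%. It has a second arm for hypersensitivity symptoms.
- The isolated-bilirubin row covers raised bilirubin with ALT below 3 x ULN. Part (1) says no dose change is needed, provided ALT is not raised and nothing else points to liver injury. Part (2) calls for fractionation above 1.5 x ULN and adds: "If bilirubin is >35% direct (conjugated), further evaluation for underlying cause of cholestasis should be performed".

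**Section 15.** Section 15.15(c) says "Patients who have AST/ALT >3 X ULN and concurrent bilirubin >2 X ULN must permanently discontinue pazopanib". The nursing guideline at 15.28 says "Patients who have AST/ALT levels > 3x ULN and concurrent bilirubin >2X ULN should permanently discontinue pazopanib". Neither has a direct-bilirubin condition.

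**Section 10.51.** The liver chemistry rows of the reporting table are also triggered by ALT only.

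No clause says whether Section 8 or Section 15 governs when they differ.

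**The concern.** A raised transaminase together with raised conjugated bilirubin is the liver signal for which both sections prescribe a permanent stop. Section 8.4 recognises it only when the transaminase is ALT. Section 15 names AST as well. A physician using the dose-modification table and a nurse using the nursing guideline could each follow the protocol and act in opposite ways on the same result.

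More than the dose is at stake. When row D is not met, its other actions are not triggered either: recall within 24 hours, hepatology consult, PK sample, viral serology, autoantibodies, creatine phosphokinase and liver imaging. The liver-specific reporting row in 10.51 is not triggered, although the general SAE rules still apply.

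**Working it through.** There is no planned figure to reproduce. The check runs one illustrative patient through each rule: AST 4 x ULN, ALT 2.5 x ULN, total bilirubin 2.5 x ULN, direct 40%, no hypersensitivity symptoms.

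| Provision | Met? | Instruction |
|---|---|---|
| 15.15(c), either-enzyme reading | Yes (AST 4 > 3; bilirubin 2.5 > 2) | Must stop permanently |
| 15.28, same reading | Yes | Should stop permanently |
| 8.4 row A | Yes (ALT 2.5 ≤ 3.0) | Continue at current dose |
| 8.4 rows B, C | No (ALT not > 3.0) | None |
| 8.4 row D | No (ALT not > 3.0) | None |
| 8.4 isolated-bilirubin row, part (1) | Doubtful: AST of 4 x ULN can count as another sign of liver injury | The no-change assurance may lapse, but no stop replaces it |
| 8.4 isolated-bilirubin row, part (2) | Yes, unless its no-ALT-elevation wording is read strictly (ALT is above normal but below 3) | Cholestasis evaluation, no stop |
| 8.3, 8.12 and 8.2 residual rows | Depends on grade and clinical significance | Grade 2 or 3: interrupt, omit or hold (8.3 restarts 200 mg lower). Grade 4: discontinue |
| 7.4 | Only after a Grade 3 or 4 break of 28 days or more without restart | Discontinue, but not on detection |

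CTCAE cut-offs are not in the documents, so no grade is assigned to this patient.

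**If the slash means both enzymes**, ALT 2.5 fails 15.15(c) and 15.28, and the conflict disappears.

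**Scale.** The joint rate is not given. Table 79 (Appendix VIII) reports any-grade total bilirubin increase in 36% and any-grade AST increase in 53% of pazopanib patients, so it bounds the joint rate only loosely. Grade 3 AST was less frequent than Grade 3 ALT (7% v 10%). Section 8.4 also notes that pazopanib can raise indirect bilirubin without liver injury, and such a rise would not meet the direct >35% condition. For illustration only, with n = 39 (the 35 evaluable plus 4 additional patients in 16.22) and an assumed joint rate p, the chance of at least one such patient is 1 − (1 − p)^39:
- p = 0.1%: 3.8%
- p = 0.5%: 17.8%
- p = 1%: 32.4%

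These rates are assumptions. The point rests on the conflicting text.

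**Checking the proposed wording.**
- The patient above: AST 4 > 3.0, bilirubin 2.5 ≥ 2.0, direct 40% > 35%. Row D is met, row A yields, and 8.4 agrees with Section 15.
- AST 4, ALT 2, bilirubin 1.8, direct 40%: row D is not met because 1.8 < 2.0. The cholestasis evaluation must survive for this patient, so the whole isolated-bilirubin row should not be restricted to AST ≤3.
- AST 4, ALT 2.5, bilirubin 2.5, direct 30%: row D is not met, and 15.15(c) still says stop. This difference remains.

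**The case against.** The strongest objection is that the conflict depends on an undefined slash. That is true. A both-enzymes reading would make 15.15(c) miss a patient with ALT alone above 3 x ULN, whom row D stops. But this argument assumes that 15.15(c) was meant to mirror row D. The two already differ, since 15.15(c) has neither a direct-bilirubin condition nor a hypersensitivity arm. Either enzyme remains the ordinary reading, but it is not proven.

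A second objection is that row A is not all that 8.4 says about this patient. The no-change assurance in the isolated-bilirubin row carries its qualifier about other evidence of liver injury. The residual rows and 7.4 can lead to interruption or discontinuation. Section 15.15(c) adds "Use of pazopanib is not recommended in patients with total bilirubin >3 X ULN (regardless of any ALT"), and footnote b of 8.4 calls for an SAE report: "If testing is unavailable and a subject meets the criterion of total bilirubin >1.5 x ULN, then the event should be promptly reported". All of this stands as mitigation. A reader might infer that 8.4 plainly orders treatment to continue with nothing to temper it, and the documents do not support that. They support only the narrower statement that row A's trigger is met and that no Section 8 provision orders the permanent stop on detection, apart from Grade 4.

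A reader might also infer an AST gap from 3.16, which disallows "Concomitant elevations in bilirubin and AST above" the upper limit of normal at entry, while row A keeps a patient with much higher values on drug. That contrast proves nothing specific to AST. Section 3.16 has the same note for ALT, and entry limits are often stricter than on-treatment limits.

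Finally, ALT is used consistently in rows A to D and in 10.51, which may be deliberate. If so, Section 15 needs the correction, and the protocol should say so.

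**Conclusion.** The point holds, conditional on reading the slash as either enzyme. For AST >3, ALT ≤3 and total bilirubin >2 x ULN with direct >35%, 15.15(c) requires permanent discontinuation, row A says continue, row D is not met, and nothing ranks the two sections. The mitigating provisions reduce the practical risk without resolving the conflict.

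The issue is small in frequency and confined to patient safety instructions. The combination is rare and no rate can be estimated from the documents. A reader might infer that the efficacy result is at risk. It is not: the 12-month survival endpoint counts deaths and losses to follow-up as failures, whatever the dosing. Nor does the exclusion of abnormal liver function tests from the 16.42 stopping rule show that such events would go unseen. That rule concerns Grade 4 or higher events, the study team may suspend accrual at its discretion, AST and bilirubin are graded at each evaluation (10.6), and the DSMB reviews safety at least twice a year.

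This should be corrected because it is a contradictory dosing instruction that is cheap to remove. It does not undermine the trial.

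**What to change.** 1. In the bilirubin arm of row D, and in the matching liver row of 10.51, write: ALT or AST >3.0 x ULN with total bilirubin ≥2.0 x ULN and direct >35%. Leave the hypersensitivity arm on ALT.
2. State that row A applies only when row D is not met. Leave rows B and C unchanged.
3. In the isolated-bilirubin row, limit only the sentence saying that no dose change is needed to patients with both ALT and AST ≤3 x ULN. Keep part (2), fractionation and cholestasis evaluation, for all patients with ALT <3 x ULN whatever the AST.
4. Cross-refer 15.15(c) and 15.28 to row D for this combination.
5. Separately, state which rule governs when direct bilirubin is ≤35%. Section 15.15(c) has no direct-bilirubin condition and 8.4 does, and items 1 to 4 do not settle that.

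If the sponsor intended both enzymes in Section 15, it should say so there instead.

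The cost is amendment wording. AST is already drawn with ALT and bilirubin (4.0, footnotes 1 and 9). The downside is that an occasional AST rise of non-hepatic origin, such as muscle, with conjugated hyperbilirubinemia will trigger the stop and work-up. Row D has no re-challenge step, so that patient loses the drug. Row D's creatine phosphokinase test would help identify such a case.
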